12.3.3.1 Analysis of Primary Efficacy Variables

The primary efficacy endpoint is the change from baseline in UEMS at 6 months after treatment. The null hypothesis to be tested is that the mean change from baseline in UEMS at 6 months after treatment is the same for 9-mg dose of VX-210 and placebo.

The primary analysis will be based on a mixed-effects model for repeated measures (MMRM). The model will include the change from baseline in UEMS as the dependent variable; treatment, visit, and treatment-by-visit interaction as fixed effects; and subject as a

random effect, with adjustment for age and AIS grade (A versus B with sacral pinprick preservation versus B without sacral pinprick preservation) at baseline. In the model, visit will be treated as a class variable, and an unstructured covariance matrix will be assumed to model the within-subject variability. This model imposes no assumptions on the correlation structure and is considered robust. Denominator degrees of freedom for the F-test for fixed effects will be estimated using the Kenward-Roger approximation.⁵² With a mixed-effects model based on restricted maximum likelihood estimation as the primary analysis and assuming that, conditional on fixed and random effects, data are missing at random, no imputation of missing data will be performed.

The primary result obtained from the model will be the estimated mean treatment effect at 6 months after treatment. The estimated mean treatment effect, a 95% CI, and a 2-sided *P* value will be provided. Furthermore, the treatment effect at each postbaseline visit, obtained from the model, will also be provided.

If there is a convergence problem due to the use of an unstructured covariance matrix, the unstructured covariance matrix will be replaced by a compound symmetric covariance matrix to model the within-subject errors.

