4 INTRODUCTION

This statistical analysis plan (SAP) is for the final analysis and interim analysis (IA) of study VX15-210-101 and is based on the

- approved clinical study protocol, 14 April 2017, Version 2.0
- approved eCRF, dated May 24 2018, Version 4.0

VX15-210-101 is a Phase 2b/3, double-blind, randomized, placebo-controlled multicenter study. This study will assess the efficacy and safety of VX-210 in subjects with acute traumatic cervical spinal cord injury.

This SAP (Methods) documents the interim and final efficacy and safety analysis and data presentation for VX15-210-101.

SAS® Version 9.4 Software (SAS Institute, Cary, North Carolina, USA) or higher will be used to generate all statistical outputs (tables, figures, listings and datasets).

The SAP (Methods) Version 1.0 was finalized and approved before the data cut for the interim analysis. The interim analysis methods specified in Section 10.1 of the SAP (Methods) Version 1.0 were implemented during the interim analysis. Any revisions to the approved SAP (Methods) Version 1.0 will be documented and approved prior to the final clinical database lock and treatment unblinding for the study.

Any changes made to the SAP (Methods) after the clinical data lock has occurred will be documented in the clinical study report for this study.

The analysis addressing the pharmacokinetic (PK) objective of the study will be described in the Clinical Pharmacology Analysis Plan (CPAP) which will be developed separately by the Clinical Pharmacology department at Vertex Pharmaceuticals Incorporated (Vertex). The independent data monitoring committee (IDMC) analyses are also described in a separate SAP.

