7.2 Sample Size and Power

The primary efficacy endpoint is the change from baseline in UEMS at 6 months after treatment.

The null hypothesis to be tested is that the mean change from baseline in UEMS at 6 months after treatment is the same for 9-mg dose of VX-210 and placebo. This null hypothesis will be tested at 2-sided significance level $\alpha = 0.05$.

The sample size was calculated using a projected standard deviation (SD) of 6.0, based on the variability of improvement in UEMS scores of cervical subjects in the historical Sygen database. Anticipated withdrawal of 10% of subjects before the first follow-up assessment was also included in the sample size calculation.

If 9-mg dose group improves in UEMS by 4 points over placebo (a clinically meaningful increase), a total of approximately 100 subjects (approximately 50 per arm) will have approximately 82.1% power to detect a statistically significant treatment effect for 9-mg dose group compared to placebo, considering the interim futility analysis.

Based on the review of data from Anderson et al., the SD was projected to be 3.8 for SCIM III Self-Care subscore. [Table 7-1](#) presents the estimated power for detecting various

treatment differences between an active treatment group and the placebo group in SCIM III Self-Care subscore, assuming 45 randomized subjects with follow-up assessment in each treatment group without considering the possible power loss from the interim futility analysis.

Table 7-1 Power Estimates Under a Variety of Treatment Differences, Given 45 Randomized Subjects With Follow-up Assessments in Each Treatment Group

Mean Difference in SCIM III Self-Care Subscore	Power (%)
1	23
2	69
3	95

Power estimates are based on 2-sided t-test with $\alpha = 0.05$.

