9.3.1.2 Primary Analysis

The UEMS score will be summarized at baseline, 6 weeks, 3 months, 6 months, and 12 months after treatment using the descriptive summary statistics by treatment group. The change from baseline in the UEMS score at 6 weeks, 3 months, 6 months, and 12 months after treatment will also be summarized descriptively by treatment group.

The primary efficacy endpoint is the change from baseline in the UEMS score at 6 months after treatment. The null hypothesis to be tested is that the mean change from baseline in the UEMS score at 6 months after treatment is the same for 9 mg dose of VX-210 and placebo.

The primary efficacy analysis will be based on an MMRM model. The model will include the change from baseline in the UEMS score at 6 weeks, 3 months, 6 months, and 12 months after treatment as the dependent variable; treatment, visit, and treatment-by-visit interaction as fixed effects; and subject as a random effect, with adjustment for age and AIS grade (only including A versus B with sacral pinprick preservation versus B without sacral pinprick preservation) at baseline. In the MMRM model, visit will be treated as a class variable, and an unstructured covariance matrix will be assumed to model the within-subject variability. Denominator degrees of freedom for the F-test for fixed effects will be estimated using the

Kenward-Roger approximation. If change from baseline in the UEMS score is missing after the visit windows rules have been applied, the missing value will be assumed to be MAR conditional on the observed data. With an MMRM model based on restricted maximum likelihood estimation as the primary efficacy analysis and under the MAR assumption, no imputation of missing data will be performed.

The primary result obtained from the primary efficacy analysis will be the estimated mean treatment effect (Least Squares [LS] means difference) at 6 months after treatment. The estimated mean treatment effect at 6 months after treatment, a 95% confidence interval (CI), and a 2-sided *P* value will be provided. Furthermore, the estimated mean treatment effects (with 95% CI) at 6 weeks, 3 months, and 12 months after treatment, obtained from the model established, will also be provided.

If there is a convergence problem due to use of an unstructured covariance matrix, the unstructured covariance matrix will be replaced by a compound symmetric covariance matrix to model the within-subject variability.

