10 SUMMARY OF INTERIM AND IDMC ANALYSES

10.1 Interim Analysis

An interim analysis will be conducted when approximately 33% of enrolled subjects have completed the 6-month follow-up visit. Based on the results of this interim analysis, the study may continue or stop for futility. The IDMC will conduct review of this interim analysis and make recommendation to the sponsor. If the study is considered unsuccessful at the time of the interim analysis, the study is to be terminated, study enrollment is to be stopped, and subjects are to be followed for safety reasons only.

Based on the review of the data provided at the interim analysis meeting, the IDMC will make a recommendation regarding whether the study should continue or should stop for futility. The guideline for futility stopping will be that the 9-mg dose group improves in UEMS by less than approximately 1.19 points over placebo for the approximately 33% of subjects analyzed, under the assumed standard deviation (SD) of 6.

The IDMC will review the observed SD at the time of the interim analysis. If the SD deviates from the assumption, the futility guide is adjusted to be that the study will be stopped for futility if conditional power (under observed primary endpoint treatment effect size) is <10.6% or the observed primary endpoint treatment effect size is <1.19. The following table presents examples of the futility boundary with respect to different sizes of SD. The last column refers to the minimum observed primary endpoint effect size that is required to achieve statistical significance under the given size of SD at the final analysis.

Table 10-1 Guidelines for Futility Stopping

Standard Deviation	Futility Boundary	Conditional Power (Under	Minimum Required Observed
---------------------------	--------------------------	---------------------------------	----------------------------------

		Observed Effect Size)	Effect Size at Final Analysis
4	1.19	25.1%	1.7
6	1.19	10.6%	2.5
8	1.59	10.6%	3.3
10	1.98	10.6%	4.1

In all analyses supporting this interim analysis, only the first 43 randomized subjects will be used unless otherwise specified; this sub-population includes approximately 33% of enrolled subjects who are dosed with placebo or 9-mg of VX-210 and who will have completed the 6-month follow-up visit at the time of the interim analysis data cut.

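### If the unstructured MMRM fails to converge, the only fallback is compound symmetry, whose single variance for all four visits can misstate the 6-month standard error (minor; very unlikely to be triggered)

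*SAP*

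**What the plan says.** SAP 9.3.1.2 fits the change in UEMS at 6 weeks, 3, 6 and 12 months with an unstructured within-subject covariance and Kenward-Roger degrees of freedom. The primary result is the treatment difference at 6 months. Should that covariance keep the model from converging, the rule is that the "unstructured covariance matrix will be replaced by a compound symmetric covariance matrix to model the within-subject variability". Protocol 12.3.3.1 has the same rule: the unstructured matrix "will be replaced by a compound symmetric covariance matrix to model the within-subject errors".

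Both sentences are complete and unredacted. The readable text names no intermediate structure, no version with a separate variance per visit and no empirical standard error. The protocol defends the unstructured matrix on the ground that it assumes nothing about the correlation structure.

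The only variability figure for UEMS change is in SAP 7.2 (and Protocol 12.1): "The sample size was calculated using a projected standard deviation (SD) of 6.0". No SD is given for any individual visit.

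**The concern.** Compound symmetry has two parameters: one variance shared by all visits and one correlation. The plan would therefore move in a single step from a model with no covariance assumptions to one that requires the spread of UEMS change to be the same at 6 weeks and at 12 months. If the spread differs by visit, the pooled variance is wrong for the 6-month visit, and so are the standard error, the 95% CI and the P value for the primary endpoint. Kenward-Roger is a small-sample adjustment that takes the covariance model as correct, so it does not repair a wrong structure.

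If the SE is too small, the nominal level rises above 5%. If it is too large, power is lost.

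**Working it through.** **Inputs from the documents.** SD 6.0 for UEMS change; about 50 per arm with 10% withdrawal, hence about 45 per arm; two-sided alpha 0.05 (SAP 7.2); four visits in the model (SAP 9.3.1.2); futility boundary 1.19 points at about one third of subjects (SAP 10.1).

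**Assumption.** The SDs at 6 weeks, 3 and 12 months are not documented and are varied below. The 6-month SD is held at 6.

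**The plan's own figures.**
- True 6-month SE = 6 × sqrt(2/45) = 1.265.
- Smallest significant difference = 1.96 × 1.265 = 2.48. SAP Table 10-1 gives 2.5 at SD 6.
- Power for 4 points is 88.5% without the futility look and 82.6% with it (15 per arm at the interim, boundary 1.19). The plan states 82.1%.

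The inputs are therefore read correctly, and the stated power is not in question.

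**Effect of the fallback.** With complete data and no covariates, the 6-month estimate is the difference of the arm means under any covariance structure; only its SE changes. The REML common variance under compound symmetry is the mean of the four visit variances. So:

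- r = SE(compound symmetry) / true SE = sqrt(mean visit variance / 36)
- nominal two-sided level = 2 × P(Z > 1.96 r)
- smallest significant difference = 2.48 × r (2.479 before rounding)

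Example, SDs 4/5/6/7: mean variance = (16 + 25 + 36 + 49)/4 = 31.5; r = sqrt(31.5/36) = 0.935; level = 2 × P(Z > 1.833) = 6.7%.

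| Assumed SDs (6 wk/3/6/12 mo) | Mean variance | r | Level, closed form | Level, simulated with age and AIS grade | Smallest significant difference |
|---|---|---|---|---|---|
| 6/6/6/6 | 36 | 1.000 | 5.0% | 5.0% | 2.48 |
| 4/5/6/7 | 31.5 | 0.935 | 6.7% | 6.9% | 2.32 |
| 3/4.5/6/6.5 | 26.875 | 0.864 | 9.0% | 8.9% | 2.14 |
| 4/5/6/8 | 35.25 | 0.990 | 5.2% | not run | 2.45 |
| 5/5.5/6/8 | 38.8125 | 1.038 | 4.2% | 4.1% | 2.57 |

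The simulations used 40,000 null trials per pattern, 45 per arm, complete data and assumed correlation 0.85^lag (constant 0.75 for equal SDs); Monte Carlo SE was 0.10 to 0.14 points. The SE is too small when the mean visit variance is below 36 and too large when it is above. All these levels assume the fallback is used and ignore the futility look.

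**How often the fallback would be used.** The unstructured matrix has 10 parameters for about 90 subjects. In simulated fits with age and AIS grade and monotone dropout, 150 of 150 converged at 45 per arm and 150 of 150 at 30 per arm. A harder model that added a random subject effect converged in 300 of 300. Zero failures in 300 gives a 95% upper bound of 1 − 0.05^(1/300) = 1.0%. If the level were 9.0% under the fallback and 5.0% otherwise, the procedure as a whole would have level 0.01 × 9.0% + 0.99 × 5.0% = 5.04%. At an assumed 5% failure rate it would be 0.05 × 9.0% + 0.95 × 5.0% = 5.2%. These fits used a generic optimiser, not SAS, and assumed covariances.

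**Alternatives.** Simulated levels with complete data, no covariates and the same 0.85^lag correlation (8,000 null trials each, Monte Carlo SE about 0.25 points), for 4/5/6/7, 3/4.5/6/6.5 and 5/5.5/6/8 in turn:
- heterogeneous Toeplitz: 4.8%, 5.0%, 5.3%
- heterogeneous AR(1): 4.9%, 4.8%, 4.7%
- heterogeneous compound symmetry: 6.2%, 5.0%, 5.9%

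The first two structures contain the assumed correlation, so the check favours them. For heterogeneous compound symmetry the large-sample SE is about 2.2% too small in all three patterns: 2 × P(Z > 1.96 × 0.978) = 5.5%.

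**The case against.** The strongest reply is that this almost never matters. The trigger is rare, the 6.7% and 9.0% describe a trial in which compound symmetry is always used, and the visit SDs behind them are assumed. A pattern such as 4/5/6/8 is almost harmless. All of this stands, and it is why the point is minor. A reader might infer that the plan inflates the type I error of the primary test to 9%. The documents do not support that: they give no visit SDs, the error can go either way, and the primary result is untouched if the unstructured model converges.

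A second reply is the futility rule: "The guideline for futility stopping will be that the 9-mg dose group improves in UEMS by less than approximately 1.19 points over placebo". The interim z boundary is 1.19/(6 × sqrt(2/15)) = 0.543, so about 71% of null trials would stop. If the rule were always followed, overall two-sided rejection would be 2.1%, 2.8%, 3.6% and 1.8% for 6/6/6/6, 4/5/6/7, 3/4.5/6/6.5 and 5/5.5/6/8. This is correct, but the rule is a guideline for an IDMC recommendation, so error control should not rest on it. Nor does it correct the width of the final confidence interval.

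Third, the proposed last resort is imperfect. Under 4/5/6/7, heterogeneous compound symmetry gave 6.2% against 6.8% for plain compound symmetry in the same setting. Under 5/5.5/6/8 it gave 5.9% against 4.3%, turning a conservative test slightly liberal. That stands, and it is why this structure comes last. How the alternatives converge once the unstructured fit has failed was not tested.

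Fourth, the planned summaries by visit would show unequal SDs, and redacted text in SAP 9.3 may hold supportive analyses. Neither changes the stated rule, and changing the structure after seeing unblinded summaries would be post hoc.

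Finally, a reader might infer that naming subject as a random effect beside an unstructured matrix would itself trigger the fallback. The check does not support this: 300 of 300 such fits converged, with the 6-month variance within 0.1% of the unstructured estimate. It is not part of this point.

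**Conclusion.** The point holds as a minor one. The plan has a single, unredacted fallback that imposes a common variance and can give the wrong 6-month SE. Its direction and size cannot be determined from the documents. If the fallback were used, the assumed patterns give SE ratios from 0.864 to 1.038 and nominal levels from about 4% to 9%; with equal variances and complete data there is no error. Allowing for how rarely the fallback should be needed, the effect on the procedure as a whole is likely to be very small.

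These figures rest on a 6-month SD of 6, 45 per arm, complete data, assumed SDs at the other visits and, for the simulations, assumed correlations. With missing data a wrong covariance could also shift the estimate itself; that was not quantified.

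**What to change.** Before final lock and unblinding, replace the compound symmetry fallback with a pre-specified ordered list of structures that keep a separate variance for each visit. One example is heterogeneous Toeplitz, then heterogeneous AR(1), then heterogeneous compound symmetry as a last resort, noting that the last may remain slightly anti-conservative (about 5.5% in large samples under the assumed correlations). Use Kenward-Roger degrees of freedom throughout and report which structure was used. The exact order is a matter of choice; fixing it in advance is what matters.

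Make the same change in Protocol 12.3.3.1, or record it in the SAP as a change from the protocol, so that the two documents agree on the primary analysis.

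The cost is a small change in wording and programming, with no new data. SAP section 4 leaves room for it: "Any revisions to the approved SAP (Methods) Version 1.0 will be documented and approved prior to the final clinical database lock".

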9.3.2 Analysis of Secondary Efficacy Variables

9.3.2.1 Secondary Analyses

Secondary efficacy endpoints will be summarized using descriptive summary statistics by treatment group and all post-baseline follow-up visits (AIS grade and motor level will also be summarized descriptively at baseline).

- SCIM III Self-Care subscore at 6 months after treatment: The range of the SCIM III Self-Care subscore is 0-20. The score collected in the CRF will be directly used in the analysis. The SCIM III Self-Care subscore at 6 weeks, 3 months, 6 months, and 12 months after treatment will be summarized descriptively by treatment group.
- CUE-T score at 6 months after treatment: The range of the CUE-T score is 0-128. The score collected in the CRF will be directly used in the analysis. The CUE-T score at 6 months after treatment will be summarized descriptively by treatment group.

- GRASSP Quantitative Prehension score at 6 months after treatment: The GRASSP Quantitative Prehension score will be derived as described in Appendix F. The range of the score is 0-60. The GRASSP Quantitative Prehension score at 6 months after treatment will be summarized descriptively by treatment group.
- AIS grade conversion from baseline at 6 months after treatment: An AIS responder is defined as a subject with improvement by ≥ 2 AIS grades (i.e., baseline AIS grade A changed to grade C, D, or E; baseline AIS grade B changed to D or E at 6 months after treatment). The AIS grade at baseline, 6 weeks, 3 months, 6 months, and 12 months after treatment will be summarized descriptively by treatment group. The AIS responder, defined as aforementioned, at 6 weeks, 3 months, 6 months, and 12 months after treatment will also be summarized descriptively by treatment group.
- Motor level change from baseline at 6 months after treatment: A motor level responder is defined as a subject with improvement by ≥ 2 motor levels on either side of the body (i.e., baseline level C4 changed to C6, C7, C8 on the left; or baseline level C5 changed to C7, C8... on the right and so on). A subject with a missing/not determined motor level on one side of the body for a given visit and an improvement of ≥ 2 motor levels on the other side of the body at that visit will be classified as a responder for that visit; for all other cases in which one or both motor levels are missing/not determined at a given visit, the responder result at that visit will be noted as 'missing'. The motor level at baseline, 6 weeks, 3 months, 6 months, and 12 months after treatment will be summarized descriptively by treatment group. The motor level responder, defined as aforementioned, at 6 weeks, 3 months, 6 months, and 12 months after treatment will also be summarized descriptively by treatment group.

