versus B without sacral pinprick preservation) at baseline. The primary result obtained from the model will be the treatment effect at 6 months after treatment. Statistical significance for the primary efficacy endpoint will be tested between 9-mg dose group and the placebo group at significance level $\alpha = 0.05$.

Secondary Analyses: To control the type I error rate, a hierarchical testing procedure will be used for the important efficacy endpoints. At each step, the test for treatment effect will be considered statistically significant if the test meets the criteria for significance and all previous tests are also statistically significant. The first endpoint in the testing hierarchy will be the primary endpoint (change from baseline in UEMS at 6 months after treatment). The second endpoint in the testing hierarchy will be the SCIM III Self-Care subscore at 6 months after treatment.

IDMC Reviews Safety and tolerability data will be reviewed by an independent data monitoring committee to ensure the safety of the subjects in the study.
Results of an interim analysis for futility will be reviewed by the IDMC.

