12.3.3 Efficacy Analysis

Assessment of efficacy of VX-210 treatment is 1 of the primary objectives of this pivotal study. A hierarchical testing strategy will be used to preserve the overall 2-sided type I error rate at the 0.05 level. All efficacy endpoints will be analyzed based on the FAS.

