12.3.3.2 Analysis of Secondary Efficacy Variables

For all secondary efficacy variables, the primary analysis will focus on the treatment effects at 6 months after treatment.

- SCIM III Self-Care subscore at 6 months after treatment: The analysis of this variable will be based on an analysis of covariance (ANCOVA) model, which will include the SCIM III Self-Care subscore at 6 months after treatment as the dependent variable, and treatment as a fixed effect, with adjustment for age and AIS grade (A versus B with sacral pinprick preservation versus B without sacral pinprick preservation) at baseline. If the SCIM III Self-Care subscore at 6 months after treatment is missing, the score at the Early Termination Visit will be carried forward for the analysis.
- CUE-T score at 6 months after treatment: The analysis of this variable will be similar to the analysis of the SCIM III Self-Care subscore.
- GRASSP Quantitative Prehension score at 6 months after treatment: The analysis of this variable will be similar to the analysis of the SCIM III Self-Care subscore.
- AIS grade conversion from baseline to 6 months after treatment: The response variable will be analyzed using the 2-sided Cochran-Mantel-Haenszel (CMH) test stratified by age (<30 versus ≥30 years of age) and AIS grade (A versus B with sacral pinprick preservation versus B without sacral pinprick preservation).
- Motor level change from baseline to 6 months after treatment: The analysis of this response variable will be similar to the analysis of the AIS grade conversion from baseline to 6 months after treatment.

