12.3.3.4 Adjustment for Multiple Comparisons

The multiplicity adjustment will control the overall 2-sided type I error rate at 0.05 for testing 9-mg of VX-210 versus placebo for multiple endpoints.

The following multiplicity adjustment approach will be used to strongly control the overall 2-sided type I error rate at 0.05 for the primary endpoint and key secondary endpoints.

A hierarchical testing procedure will be used for the multiple endpoints at the 2-sided significance level $\alpha = 0.05$ as follows:

Step 1: The primary efficacy endpoint will be tested at significance level $\alpha = 0.05$.

Step 2: If VX-210 is statistically significant at $\alpha = 0.05$ from Step 1, the first key secondary efficacy endpoint will be tested at $\alpha = 0.05$.

At each step, the test for treatment effect will be considered statistically significant if the test meets the criteria for significance and all previous tests are also statistically significant. The first 2 layers of the testing hierarchy are as follows:

1. Change from baseline in UEMS at 6 months after treatment
2. SCIM III Self-Care subscore at 6 months after treatment

After the primary (change in UEMS) and first key secondary endpoint (SCIM III Self-Care) have met the level of significance for VX-210 compared to placebo, additional functional tests will be added to this hierarchy, with a test for treatment effect at each step that will be considered statistically significant only if the test is statistically significant and all previous

tests are also statistically significant. The hierarchy of endpoints after change in UEMS and SCIM III Self-Care subscore will be described in the SAP.

Note that the comparisons that cannot be performed formally due to hierarchical testing strategy will still be performed, and the corresponding P values will be considered descriptive.

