9.3.4 Multiplicity Adjustment

Not applicable.

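### The SAP's visible final analysis compares the arms on none of the five secondary efficacy endpoints, so the protocol's second confirmatory step (SCIM III Self-Care) has no test

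*SAP*

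**What the plan says.** **Protocol.** Section 12.3.3.2 covers all five secondary efficacy endpoints. For SCIM III Self-Care, "The analysis of this variable will be based on an analysis of covariance (ANCOVA) model", adjusted for age and AIS grade, with the early-termination score used when the 6-month score is missing. CUE-T and GRASSP Quantitative Prehension are to be handled in the same way. For AIS grade conversion, "The response variable will be analyzed using the 2-sided Cochran-Mantel-Haenszel (CMH) test stratified by age" group and AIS grade, and motor level change follows the same method.

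Section 12.3.3 states: "A hierarchical testing strategy will be used to preserve the overall 2-sided type I error rate at the 0.05 level". The synopsis adds: "The second endpoint in the testing hierarchy will be the SCIM III Self-Care subscore at 6 months after treatment". Section 12.3.3.4 tests each step at two-sided 0.05 and assigns the remainder to the SAP: "The hierarchy of endpoints after change in UEMS and SCIM III Self-Care subscore will be described in the SAP". It also says that "comparisons that cannot be performed formally due to hierarchical testing strategy will still be performed, and the corresponding P values will be considered descriptive".

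**SAP.** Section 9.3.2.1 opens: "Secondary efficacy endpoints will be summarized using descriptive summary statistics by treatment group and all post-baseline follow-up visits". Each of the five endpoints then receives a definition or score range and a by-arm descriptive summary. The section headed "9.3.4 Multiplicity Adjustment" says only that it does not apply. Section 9.3.1.2 keeps the UEMS hypothesis test with a confidence interval and P value. Section 4 names protocol Version 2.0 as the basis of the SAP.

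**The concern.** The protocol treats the SAP as the place where the testing sequence is completed. The visible SAP neither completes it nor carries out the step that the protocol has already fixed. An analyst following the SAP would produce the UEMS test and then stop, with no planned analysis for Step 2.

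At stake is the confirmatory status of SCIM III Self-Care, the only secondary endpoint that the protocol names in the sequence and a direct measure of the daily-function objective. Protocol 8.2.1 relies on the primary and secondary endpoints together to show whether the benefit is meaningful. If the tests were added only after unblinding, the order beyond SCIM III could be challenged as chosen with the results in view.

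**Working it through.** The point turns on text, so the check sets the sections side by side.

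**1. Between-arm analysis by endpoint**

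| Endpoint at 6 months | Protocol 12.3.3.2 | SAP 10.1.2 (interim) | SAP 9.3.2.1 (final, visible) |
|---|---|---|---|
| SCIM III Self-Care | ANCOVA | ANCOVA, LS means difference and 95% CI, no P value | By-arm summary |
| CUE-T | ANCOVA | As for SCIM III | By-arm summary |
| GRASSP Quantitative Prehension | ANCOVA | As for SCIM III | By-arm summary |
| AIS grade conversion | Stratified CMH | By-arm summary | By-arm summary |
| Motor level change | Stratified CMH | By-arm summary | By-arm summary |
| **Count with a between-arm analysis** | **5 of 5** | **3 of 5** | **0 of 5** |

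The sixth secondary endpoint, pharmacokinetics, is not an efficacy endpoint and goes to a separate plan (SAP section 4).

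**2. Testing sequence**

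| Step | Protocol 12.3.3.4 | SAP final analysis (visible) |
|---|---|---|
| 1. UEMS change | Two-sided 0.05 | Tested (9.3.1.2) |
| 2. SCIM III Self-Care | Two-sided 0.05, only if Step 1 succeeds | No test |
| 3 onward | Order to be set in the SAP | No order given |
| Comparisons outside the sequence | Still performed, P values descriptive | Not planned |

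**3. Is this only a matter of wording?** No. Where the SAP intends a between-arm comparison it names the model: MMRM for UEMS in 9.3.1.2, and ANCOVA for three functional scores in 10.1.2. The final analysis of those three scores therefore specifies less than the interim look did.

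**4. The SAP's SCIM III power table.** SAP 7.2 (Table 7-1) gives 23%, 69% and 95% power for differences of 1, 2 and 3 points. Inputs from that section are SD 3.8, 45 per arm and a two-sided t-test at 0.05.
- Standard error of the difference: 3.8 × √(2/45) = 0.801.
- Noncentrality (difference ÷ 0.801, 88 degrees of freedom): 1.25, 2.50, 3.74.
- Power from the noncentral t distribution: 23.5%, 69.5%, 95.9%.

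The table reproduces to within one percentage point. It describes a two-arm test that the visible final analysis does not contain.

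**5. What can still be recovered.** SAP 9.1 requires n, mean and SD for continuous variables and counts and percentages for categorical ones. Unadjusted by-arm differences can therefore be derived for all five endpoints. The adjusted ANCOVA comparisons, the stratified CMH tests and the confirmatory status of SCIM III are what is absent.

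**The case against.** **The choice may be deliberate.** SAP section 4 reports in the past tense that the interim methods were carried out, so this text postdates the interim analysis. Protocol 12.3.5.1 and SAP 10.1 foresee termination with follow-up for safety only if the interim is unsuccessful. The SAP contents skip sections 3 and 9.3.3, and blocks in 9.3 are redacted, so an explanation may sit in hidden text. This stands as a limit. It does not remove the conflict: the visible SAP does not say that secondary inference was withdrawn, still rests on protocol Version 2.0, still plans about 100 subjects and still tests the primary hypothesis.

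**Marking multiplicity as not applicable is coherent within the SAP.** With one formal test there is nothing to adjust. That is correct; the conflict is with the protocol.

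**The leftovers prove little.** The power table sits in a section that restates protocol design text, and the carry-forward rule in SAP 9.1 could apply to descriptive summaries. This is fair. Neither shows an intended test, and the finding does not depend on them.

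**Stronger readings that the documents do not support.**
- *Inflated type I error.* Five independent unadjusted tests at 0.05 would have a familywise error of 1 − 0.95⁵ = 22.6%, but the SAP plans no such tests.
- *Tests deleted after the interim result was seen.* SAP Version 1.0 is not among the documents, so it cannot be said that its final analysis contained these tests, or when or why they were left out.
- *Uncertainty about the order UEMS then SCIM III.* The protocol fixes that order, together with the SCIM III model, missing-data rule, alpha and gate. Only the later order is open.
- *A quantified loss of power.* The documents give no correlation between the endpoints and no link between their effect sizes, and any such figure would assume that the trial reaches its planned size.

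**Conclusion.** The SAP is wrong as written on this point. Its visible final analysis has no between-arm comparison or inference for any of the five secondary efficacy endpoints, against five of five in the protocol and three of five at the SAP's own interim. Step 2 of the protocol's sequence cannot be delivered from it, so SCIM III Self-Care could not be declared significant even if UEMS succeeds. The order after SCIM III, which the protocol left to the SAP, is not visible.

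The defect is limited. It cannot produce a false confirmatory claim, and it leaves the type I error rate and the UEMS conclusion unaffected. The conclusion rests on the visible text alone: nothing is claimed about SAP section 3, section 9.3.3 or the redacted blocks in 9.3. The mismatch should be fixed, but it does not threaten the primary result.

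**What to change.** Before final database lock and unblinding, reconcile the documents in one of two ways.

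- **If secondary inference is intended:** write the protocol's ANCOVA (SCIM III Self-Care, CUE-T, GRASSP) and stratified CMH (AIS conversion, motor level) analyses into SAP 9.3.2.1. In 9.3.4, replace the current entry with UEMS, then SCIM III Self-Care, then an order that the sponsor fixes in advance, and label P values outside the sequence descriptive, as protocol 12.3.3.4 requires.
- **If it was withdrawn on purpose:** record this in the SAP as a dated change and state whether it was made before or after the interim result was known. Bring the protocol's hierarchy text into line, and mark SAP Table 7-1 as not supporting a planned test. If hidden text already records the decision, only the alignment of the protocol and the table remains.

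The first route costs SAP text and a few tables. The three ANCOVAs are already specified for the interim; the CMH tests appear nowhere in the visible SAP and would have to be added. The second route costs SAP text and a change to the protocol wording. Neither needs new data.
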